7.2 Biological Sample Submissions

Rev. 7/12

Pathology and blood samples should be submitted to the ECOG-ACRIN Central Biorepository and pathology Facility (CBPF) for banking per patient consent as outlined in Section [9](#).

Rev. 7/12

NOTE: It is required that biological sample submissions be logged into the ECOG-ACRIN Sample Tracking System (STS) (see Section [9.3](#))

Rev. 2/13

NOTE: [Deleted in Addendum #3]

NOTE: Institutions outside of the United States and Canada must confer with the receiving laboratory and the ECOG-ACRIN Operations Office - Boston regarding logistics for submission of fresh samples.

Rev. 7/12

Biological Samples	Step 1: Registration	Step 2: Randomization ³	Six (6) Months Post Randomization	Twelve (12) Months Post Randomization
Submit from patients who answer "YES" to " I agree my tissue will be submitted for research. "				
Block from Primary Tumor	X ¹	Arm B (Surgical Specimen) Arm A (Palliative Care Surgical Specimen)		
Block from Metastatic Site	X ²			
Submit from patients who answer "YES" to " I agree biopsies may be done to obtain research specimens " at sites that have met the guidelines outlined in Section 9.4 ⁵				
Block from Primary Tumor		Arm A ³		
Block from Metastatic Site		X ⁷		
Submit from patients who answer "YES" to " I agree to provide additional blood for research. " Collection and shipping kits are available ⁴				
Peripheral Blood: DNA PAXgene or ACD tube, (1) 8.5mL		Sample may be drawn any time while participating in the protocol, although baseline (prior to treatment) preferred		
Serum: SST Red/Grey Marble top tube, (1) 10mL		X	X	X
Plasma and residual cells: EDTA Purple top tube (1) 10mL		X	X	X

1. Time of diagnosis/staging, prior to beginning induction systemic therapy.
2. If available/feasible from both Arm A and Arm B participants. Submit per patient consent. If not considered clinically necessary will qualify for research biopsy rates as outlined below.
3. Collect at the time of local therapy/at randomization for Arm B patients. For Arm A patients collect within three (3) months of randomization. If palliative surgery is performed for Arm A patients, the primary tumor block should be submitted.

4. To order kits, complete the E2108 Collection and Shipping Kit Order Form ([Appendix VI](#)) and Fax to Zemotak – International at [contact].
5. Biopsy research rates and reimbursement guidelines are outlined in Section [9.4](#). Prior to recruiting patients to the additional biopsy portion, the following conditions must be met:

Rev. 2/13 a. The research rates of \$950 per breast biopsy and \$2,350 for metastatic biopsy are deemed acceptable by the IRB or central research office.

Rev. 2/13 b. The research rate is reported to the institution's financial office and an account established in the cooperative group's principal investigator's name.

Rev. 7/12 6. [Footnote deleted in Addendum #2]

Rev. 7/12, 2/13 7. Collect within three (3) months of randomization for Arms A and B, if clinically indicated or if patient consents to research biopsy.

8. Statistical Considerations

8.1 Primary Endpoint

Overall survival, defined as time from randomization to death from any cause. All patients will be followed for survival through 5 years. Cases with incomplete follow-up or without record of vital status will be censored at the date of last contact.

8.2 Secondary Endpoints

8.2.1 Uncontrolled Chest Wall Disease

The chest wall/breast will be called “controlled” if there is no clinical or radiological evidence of the local tumor; or if there is evidence of the primary tumor but no skin nodules, ulceration, or chest wall fixation. Time to uncontrolled chest wall disease is defined as time from randomization to the development of uncontrolled chest wall disease. Patients with controlled chest wall will be censored at the last date of evaluation.

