3.1 Registration (STEP 1)

Rev. 7/12 3.1.1 Patients (male or female) must be older than 18 years and must have an intact *primary* (not recurrent) invasive carcinoma of the breast. Biopsy confirmation of the primary tumor should be by needle biopsy (preferred); incisional surgical biopsy is allowed as long as there is residual palpable or imageable tumor in the breast.

3.1.2 Patients with synchronous contralateral invasive breast cancer are excluded.

Rev. 7/12 3.1.3 Patients should have at least one organ system involved with distant metastatic disease. If only a single metastatic lesion is present, biopsy is mandatory. See Section [6](#)

Rev. 4/14 3.1.4 Baseline studies must be performed 8 weeks prior to the start of systemic therapy, and must document the extent of disease in the breast; the specifics of this are at physician discretion, but must address clinical signs and symptoms (see Section 7.1). If pre-therapy scans were not performed, scans performed within the first 4 weeks

of systemic therapy, but prior to registration, will be accepted. Radiology reports documenting status of disease must be available.

Rev. 4/14 3.1.5 If palliative radiation to non-breast sites is required prior to initiation of systemic therapy, scans may be completed within 8 weeks prior to or 4 weeks following the start of radiation therapy.

Rev. 7/12 3.1.6 If patient has only one metastatic lesion/focus, this must be proven by biopsy and the pathology report confirming the diagnosis of primary breast cancer, as well as the metastatic site, must be available.
Single metastatic lesion? _____ (Yes/No) Biopsy? _____ (Yes/No)

Rev. 7/12 3.1.7 Patients may have had prior non-invasive (DCIS) cancer if there has been no recurrence; prior ipsilateral invasive cancer also allowed if more than 5 years previous.

 3.1.8 Patients with a history of other primary cancers are eligible if the pathology report confirming the diagnosis of primary breast cancer is available and the other primary cancer was curatively treated with a 5-year disease-free interval.

Rev. 4/15 3.1.8.1 Patients with non-melanoma skin cancer are eligible; however, patients with squamous cell carcinoma of other sites (except in-situ cervix) are not eligible.

 3.1.9 Women of childbearing potential and sexually active males must be strongly advised to use an accepted and effective method of contraception.

 3.1.10 Patients with CNS metastases are eligible (as long as projected survival is > 6 months).

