5.1.2.2 Arm B: Early Local Therapy

Surgery is to occur no later than 10 weeks after randomization.

Surgical treatment will be chosen by patient and physician according to the criteria that are generally accepted for breast conserving therapy (BCT) or total mastectomy

Rev. 7/12
Rev. 4/14
Rev. 4/14

Rev. 7/12

(TM). If BCT is chosen, free surgical margins must be achieved with re-excision or mastectomy (no minimum margin width is required). Axillary management should parallel that used for non-metastatic breast cancer. Axillary dissection is required if clinical and radiologic evaluation at initial registration was suggestive of axillary disease and axillary radiation is not planned. For women not receiving axillary dissection, sentinel node biopsy should document an axillary nodal burden of 1-2 involved lymph nodes (i.e. ACOSOG Z-11 criteria may be applied if axillary radiation is not planned). For women undergoing TM, reconstructive surgery will be allowed at the discretion of the treating physician, recognizing that this may delay the continuation of systemic therapy and complicate radiation planning. Surgical quality assurance will be coordinated with the ECOG-ACRIN Surgery Committee.

Systemic therapy may resume after recovery from surgery as directed by the treating physician. Systemic therapy will continue directed by the treating physician.

Following surgery, radiotherapy is to be given as outlined in Section [5.3](#).

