6.3 Endpoints

- 6.3.1 Local Regional Recurrence (among patients randomized to Arm B)
The new development or clinically significant increase in size of any supraclavicular, infraclavicular, internal mammary or axillary adenopathy or chest wall disease or invasive in-breast recurrence
- 6.3.2 Local/Regional Progression (among patients randomized to Arm A)
The development of symptoms leading to a decision for local therapy.
- 6.3.3 Uncontrolled Chest Wall Disease
Clinical or radiological evidence of local tumor on the chest wall or the presence of skin involvement, ulceration, or symptoms.
- 6.3.4 Distant Progression
The development of new sites of non-local/regional metastatic disease or clinically significant increase in the size of existing lesions.
- 6.3.5 Survival
Date of randomization to date of death.
- 6.3.6 Quality of Life
Quality of life endpoints will be measured using patient-reported outcomes questionnaires. Domains to be assessed and instruments to be administered include FACT-G physical and functional well-being (FACT-B TOI), and domains specific to breast cancer (FACT Breast cancer subscale).

7. Study Parameters

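### Section 8.2.1 excuses a mass without local signs only if it is the primary tumor, so the same finding after resection is an event, and 6.3.3 defines this endpoint differently

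*Combined protocol and SAP*

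**What the plan says.** Section 8.2.1 gives two routes to a controlled breast or chest wall. The first applies "if there is no clinical or radiological evidence of the local tumor". The second applies "or if there is evidence of the primary tumor but no skin nodules, ulceration, or chest wall fixation". The event is the development of uncontrolled disease, timed from randomization, and "Patients with controlled chest wall will be censored at the last date of evaluation". Uncontrolled is not defined there except as the opposite of controlled.

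Section 6.3.3 defines uncontrolled chest wall disease directly: "Clinical or radiological evidence of local tumor on the chest wall or the presence of skin involvement, ulceration, or symptoms". It makes no exception for the primary tumor, and it counts symptoms, which 8.2.1 does not mention.

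Elsewhere the protocol keeps primary and recurrent tumor apart. Eligibility criterion 3.1.1 requires an intact primary, qualified as "not recurrent) invasive carcinoma of the breast". Section 6.3.1 names the return of local tumor in Arm B as recurrence, including "chest wall disease or invasive in-breast recurrence". The Arm A counterpart in 6.3.2 is different in kind: "The development of symptoms leading to a decision for local therapy".

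Objective 2.2.1 compares time to uncontrolled chest wall disease between arms. Section 8.5 adds a Fisher's exact test of the proportion at 6 months and a two-point procedure at 18 and 30 months.

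**The concern.** The second route to controlled is open only to a tumor that is still the primary. Arm A normally keeps its primary, because local therapy there is reserved for palliation of symptoms (5.1.2.1). In Arm B the primary is excised, and with breast conservation "free surgical margins must be achieved with re-excision or mastectomy". Later local tumor in Arm B is then a recurrence in the protocol's own terms and cannot use the second route. The same physical finding would be censored in one group and counted as an event in the other.

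At stake is a between-arm comparison named as a secondary objective. A stricter threshold after resection would understate any local-control benefit of early local therapy. Because 6.3.3 gives another rule, two assessors could also code the same patient differently.

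**Working it through.** The documents state no event rate, power or significance level for this endpoint, so there is no figure to reproduce. The check is to apply each definition to the same findings.

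Rule in 8.2.1: controlled = (no local tumor) OR (primary tumor present AND no nodules, ulceration or fixation).

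| Finding | Route 1 | Route 2 | Class under 8.2.1 | Class under 6.3.3 |
|---|---|---|---|---|
| Unresected primary in breast, none of the three signs, no symptoms | no | yes | controlled | unclear: is a mass in the breast on the chest wall? |
| In-breast recurrence after conservation, none of the three signs, no symptoms | no | no | uncontrolled | unclear, same question |
| Chest wall recurrence after mastectomy, none of the three signs, no symptoms | no | no | uncontrolled | uncontrolled |
| Painful unresected primary, none of the three signs | no | yes | controlled | uncontrolled |

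Rows 1 and 2 are the same finding with opposite results under 8.2.1. Rows 3 and 4 show that 6.3.3 does not cure this: it still captures a post-mastectomy recurrence more readily than a mass in an intact breast, and it disagrees with 8.2.1 on symptoms.

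The split is by resection status. A recurrence in Arm A after palliative surgery is also uncontrolled, and an unresected primary in Arm B is excused. Section 8.4 allows for 15% crossover, summed over both directions, so resection status should still follow arm closely.

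If the second route covered any local tumor, primary or recurrent, rows 1 to 3 would all be controlled under 8.2.1.

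**Illustration of sensitivity.** All inputs here are assumptions except the total of 258 randomized patients (8.4).

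- n = 258 / 2 = 129 per arm, assuming equal allocation.
- Fisher's exact test, two-sided 5%.
- pA and pB are uncontrolled proportions under a common definition. q is the further share of Arm B counted as uncontrolled only because the mass is a recurrence.
- Power to show Arm B better = sum over all a, b of Bin(a; 129, pA) × Bin(b; 129, pB + q), taken where Fisher p ≤ 0.05 and b < a.

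| pA, pB | q = 0 | q = 2% | q = 5% | q = 10% |
|---|---|---|---|---|
| 25%, 10%: difference pA − pB − q | 15 points | 13 | 10 | 5 |
| 25%, 10%: power | 87% | 73% | 46% | 13% |
| 20%, 10%: power | 56% | 36% | 14% | 2% |
| 10%, 10%: chance of a significant result against Arm B | 1.5% | 5% | 18% | 56% |

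Of 129 patients, q = 2%, 5% and 10% are about 3, 6 and 13 (129 × 0.02 = 2.6; × 0.05 = 6.5; × 0.10 = 12.9).

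**The case against.** **The sentence may mean one tumor throughout.** Both routes sit under the subject of breast and chest wall, and could be read as a single tumor that is either absent or present without worrying signs. That reading removes the asymmetry. It is possible, but it runs against the primary/recurrent distinction in 3.1.1 and 6.3.1, and against the change of term within 8.2.1 itself. The wording should not leave it open.

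**It may be deliberate.** Arm B tests complete local therapy, and treating any regrowth afterwards as loss of control is defensible. No section says this is intended, and 6.3.1 already records recurrence separately. If it is intended, the plan should say so and interpret the comparison accordingly.

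**The affected group is narrow.** This stands. Recurrences with nodules, ulceration or fixation are uncontrolled on either wording, and nodal recurrence is not clearly within 8.2.1. Some sign-free recurrences would develop signs later and be counted anyway, only later. At 6 months the effect is likely small, because 5.2 expects Arm B to have only about finished surgery and radiation by then.

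**The illustration is not the planned analysis.** This also stands. Fisher's test is planned only at 6 months; the 18- and 30-month comparison uses a two-point procedure. The 129 per arm counts everyone randomized, with no allowance for death or missing assessments. Every reclassified case is added to Arm B and none to Arm A.

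**Conclusion.** The point holds on the literal wording of 8.2.1: a mass without the three signs is censored if unresected and an event if recurrent after resection. Section 6.3.3 adds a second, conflicting definition. The time-to-event comparison and the 18- and 30-month proportions are therefore not like for like, and the 6-month proportion is affected to a lesser degree. Under 8.2.1 the bias runs against Arm B. Its size cannot be estimated from the documents; the illustration shows only that a few percentage points could matter under the assumed rates.

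Three stronger conclusions might be inferred and are not supported:

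- *The plan sets a different threshold for each arm.* The dividing line is resection status, which follows arm only approximately.
- *An asymptomatic mass is the test case under 8.2.1.* Symptoms are not a criterion there; the three signs are.
- *A specific loss of power has been shown.* Every rate used is an assumption.

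This is a secondary endpoint. Overall survival is unaffected, and this bias cannot create a false claim of benefit for early local therapy. The change should still be made, because it is cheap and the comparison is a stated objective.

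**What to change.** In 8.2.1, replace *the primary tumor* in the second route with *tumor in the breast or chest wall, primary or recurrent*. Reconcile 6.3.3 with it so that one definition applies to both arms whatever the resection status. Editing 8.2.1 alone would leave a sign-free chest wall recurrence controlled in one section and uncontrolled in the other. The reconciled text must also settle symptoms: if they count, they should appear in both sections and apply to both arms.

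Continue to record sign-free recurrence in Arm B under 6.3.1.

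The cost is wording in two sections. Skin nodules, ulceration and chest wall fixation are already recorded under 6.2.1, so no new data item is needed. The one downside is that sign-free recurrences after resection stop counting as events for this endpoint. Section 8 plans no analysis of 6.3.1, so they should be reported descriptively. Any power figure quoted for this endpoint should be labelled as an illustration under assumed rates.

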8.2.2 Health-related Quality of Life

The FACT-Breast Trial Outcome Index will be used as the primary HRQL endpoint. FACT-B TOI scores at baseline, randomization, 6, 18 and 30 months after randomization will be calculated and compared for participants randomized to early local therapy versus palliative local therapy. The change of FACT-B TOI scores over time will be compared between treatment arms as well. For the palliative local therapy arm, the change of QOL from randomization to the time of decision for local therapy will also be measured.

8.3 Patient Registration

Rev. 4/14

Rev. 7/12

Rev. 7/13

Registration must occur prior to or within 30 weeks of initiation of systemic therapy and prior to any local therapy. Patients who have not progressed during induction systemic therapy will be randomized between the two arms: Arm A (control: delayed palliative local therapy for symptomatic local progression) and Arm B (experimental: immediate local therapy). Randomization will be conducted using permuted blocks within strata with dynamic balancing within main institutions and their affiliate networks. Institutions obtain treatment assignments through the ECOG-ACRIN web registration program. Patients who progress during induction systemic therapy will undergo therapy at their physician's direction and will be monitored for local and distant events.

8.4 Sample Size

The primary comparison will be an intention-to-treat analysis including all randomized patients. It is expected that the three-year survival in the control arm will be 30%. The primary analysis of survival will be performed using a one-sided logrank test stratified on the stratification factors including marker status and treatment plan, number of involved organ systems, using an overall type I error of 5%. Allowing for the interim analysis plan discussed below, a total accrual of 186 responders and a total information of 110 deaths is planned, to give 85% power

to detect a 19.3% difference in the three-year survival rates (i.e., 49.3 % in the experimental arm). To allow for 15% probability of crossover between two arms (sum of the probabilities of patients on the experimental arm crossing over to the control arm and vice versa), both numbers are inflated by a factor of 1.38 (based on the Lachin-Foulkes correction)(53) to a total accrual of 258 responders and a total information of 152 deaths. Assuming an exponential distribution, this difference corresponds to an improvement in median survival from 21.4 to 33.5 months. Assuming 70% of the recruited patients are eligible and responding, a total of 368 patients will be needed to accrue 258 responders. Assuming an accrual rate of 6 patients per month, 62 months of accrual will be needed. The sample size was computed using seqopr6 (part of the study design library at the ECOG-ACRIN Statistical Office).

Rev. 7/13, 4/14

8.5 Interim Monitoring and Analysis Plan

Interim analyses of survival will be performed for all semi-annual DSMC meetings beginning when approximately 23% of the planned full information (36 deaths) has been observed; continuing until either the criterion for early stopping is met or full information is reached. To preserve the overall type I error rate, critical values at the interim analyses will be determined using a truncated version of the Lan-DeMets error spending function corresponding to the O'Brien-Fleming boundary (54). Boundary values at a minimal significance less than .0005 will be truncated at .0005, with the boundary also adjusted to preserve the overall type I error rate of 5%. Under the accrual and death rate assumptions above, interim analyses would be expected to occur at 28, 34, 40, 46, 52, 58 and 64 months after activation, at information times of 23%, 33%, 43%, 54%, 65%, 77%, 89% with a final analysis at approximately 70 months after activation at 100% of the information time. Due to delays in initiation of accrual and delays in data submission and processing, it is likely that the actual analysis times will be 6-12 months later.

The study will also be monitored for early stopping in favor of the null hypothesis using Jennison-Turnbull repeated confidence interval (RCI) (52) methodology. At each interim analysis the RCI on the hazard ratio will be computed using the critical values from the error spending function. If this RCI does not include the target alternative hazard ratio of 1.57 (control/experimental), then the study would be stopped early for lack of benefit. The hazard ratio of 1.57 is attenuated for the effect of noncompliance based on Lachin-Foulkes' modified hazards (53) while the actual hazard ratio will be adjusted at the time of analysis based on actual compliance rates. If criteria for early stopping are not met, then the final analysis will be performed when approximately 152 deaths have been observed.

Secondary objectives include comparison of proportions of patients with uncontrolled chest wall, time to uncontrolled chest wall disease and HRQL between arms. The proportion of patients with uncontrolled chest wall at 18 and 30 months post randomization will also be compared using the two-point procedure described in Freidlin, Korn, and et. al. (51). The fraction of uncontrolled chestwall at 6 months post randomization will also be compared using Fisher's exact test. HRQL scores will be compared using the methods described below.

Rev. 4/14

Rev. 4/14

Rev. 4/14	8.6	HRQL Power Estimate and Analysis Plan
Rev. 4/14		Health Related Quality of Life (HRQL) will be assessed using the FACT-B TOI, FACT-G, FACT Breast cancer subscale score and the additional items added to the Breast Cancer Subscale. The average total score for each scale will be recorded for both arms at baseline, randomization, six months post-randomization, 18 months post-randomization, and 30 months post-randomization and their change over time will be compared using mixed effects models. More specifically, we will fit a model with treatment assignment, assessment time, treatment assignment by assessment time interaction and other possible predictors. If the interaction of treatment assignment and assessment time is significant, then the change of HRQL over time would be different for the two arms. This model also accommodates inter-patient variability by modeling patient-specific regression lines. If there is high proportion of informative missingness in the HRQL data, we will analyze the data using the joint modeling of longitudinal data (here, HRQL) and survival time as described in Schluchter, 1992 and Schluchter, Greene and Beck, (55, 56). We will also test whether the HRQL increase or decrease from randomization to the time of decision for local therapy for the palliative local therapy arm, using a paired t test.
Rev. 7/13		
Rev. 4/14		The primary endpoint for HRQL is FACT-B TOI. Looking at FACT-B TOI data, using a 2-sided t test at level 0.20, there is 79% power to detect a difference of 4.5 points between the two arms with SD 14 (from E2100), assuming 69% of responders who received assigned treatment (89 per arm) have HRQL data at 18 months post-randomization. The Wilcoxon Rank Sum test will be used to compare the two arms if the scores are not normally distributed.
Rev. 4/14	8.7	Correlative Science (CTC) Power estimate
Rev. 7/13		Two sample t-test/Wilcoxon test will be conducted to test whether the CTC burden at 6 months after randomization will be lower in Arm B than in Arm A. Cox proportional hazards (PH) model will be used to examine whether patients with lower CTC burden at 6 months after randomization have prolonged survival. The treatment assignment, CTC burden or possibly their interaction will be included in the Cox PH model.
Rev. 7/13		Assuming 60% of the patients would provide their CTC at 6 months after randomization, we would have 155 evaluable patients, with 77 patients per arm. Assuming the standardized difference is 0.339 (difference in mean/standard deviation; e.g. the difference in CTC at 6 months after randomization for the two arms is 1 and the SD is 3), then the given sample size will provide 77% power using a two sample t test with two-sided significance level of 0.20.
Rev. 7/13		A paired t-test/ Wilcoxon test would be used to test whether there is a reduction in CTC burden from randomization to 6 month assessments in Arm B. A Cox PH model will be conducted to evaluate whether a larger reduction in CTC predicts longer survival.
		A two sample t-test/Wilcoxon test would be used to test whether the reduction in CTC in Arm B is larger than Arm A. A Cox PH model will be used to evaluate whether a larger reduction predicts longer survival.

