Therefore, a comparison at 18 months post-randomization on the FACT-B TOI score will be used as the primary HRQL endpoint analysis. A second HRQL analysis will examine FACT-B scores at about 30 months post-randomization. We hypothesize that the HRQL for the breast/chest wall items will be better for the control arm at the 6 month timepoint, and will be better in the experimental arm at the 18 month time point. An additional timepoint for Arm A patients will be at the point of decision for local therapy. No formal comparative analysis is planned for this data, but it will serve to document the degree of symptoms that trigger the decision for palliative therapy in the control arm.

Timing of FACT-B + LS-9 Administration

Rev. 4/14
Rev. 4/14

Questionnaires*	Step 1: Registration (+/- 14 days)	Step 2: Randomization	At 6 months post randomization (+/- 14 days)	At 18 months post randomization (+/- 14 days)	At 30 months post- randomization (+/- 14 days)	At decision for early local therapy (prior to surgery – Arm A patients only) (+/- 14 days)	Approximate time to complete
FACT-B + LS-9	X	X	X	X	X	X	15 minutes

* Please note that the QOL questionnaire is only available in English.

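### The 18-month FACT-B TOI comparison is powered on 89 patients per arm, but the plan's own survival rates leave only about 71–72 alive in Arm A

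*Combined protocol and SAP*

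**What the plan says.** Section 5.2 sets the primary quality-of-life analysis: "a comparison at 18 months post-randomization on the FACT-B TOI score will be used as the primary HRQL endpoint analysis". Section 8.6 gives its power: "using a 2-sided t test at level 0.20, there is 79% power to detect a difference of 4.5 points between the two arms", with a standard deviation of 14 taken from an earlier trial of the group. The sample size behind it is stated as "assuming 69% of responders who received assigned treatment (89 per arm) have HRQL data at 18 months post-randomization". The Wilcoxon test is the fallback if scores are not normal.

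Section 8.4 sets the randomized number by inflating "to a total accrual of 258 responders and a total information of 152 deaths". It assumes three-year survival of 30% in the control arm and 49.3% in the experimental arm. Under an exponential distribution, it adds, "this difference corresponds to an improvement in median survival from 21.4 to 33.5 months".

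Other quality-of-life analyses are also planned. Section 8.2.2 says: "The change of FACT-B TOI scores over time will be compared between treatment arms as well". Section 8.6 describes a mixed model with a treatment-by-time interaction, and joint modelling of scores and survival if informative missingness is high.

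**The concern.** A patient who has died before 18 months cannot supply an 18-month score, so the number assumed to have data cannot exceed the number expected alive. Section 8.6 uses one figure for both arms and gives no completion rate among survivors. Section 8.4 expects about half the control arm to die within 21 months. The two sections therefore appear to conflict, most clearly in Arm A.

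At stake is whether the stated 79% power can be relied on. It already rests on a two-sided level of 0.20, so there is little slack. In addition, the test in the power statement uses only the 18-month scores, although the same questionnaire is collected at randomization and could be used to gain precision.

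**Working it through.** **Inputs**
- 258 randomized responders (8.4). Equal allocation is inferred from the equal per-arm counts in 8.6 and 8.7, giving 129 per arm.
- Three-year survival 30% and 49.3%; medians 21.4 and 33.5 months; exponential survival (8.4). Survival runs from randomization (6.3.5, 8.1), as does the 18-month visit.
- Difference 4.5, SD 14, two-sided level 0.20, 89 per arm, power 79% (8.6).
- Completion rates among survivors and the correlation between randomization and 18-month scores are not in the documents. The values below are assumptions.

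**1. The plan's own figures**

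0.69 × 129 = 89.0, so 89 is 69% of everyone randomized to an arm.

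Noncentrality = 4.5 / (14 × √(1/89 + 1/89)) = 4.5 / 2.099 = 2.144. Normal approximation: Φ(2.144 − 1.282) = 80.6%. The noncentral t gives 80.5%. The stated 79% is reproduced to within 2 points (85 per arm would give 79.1%).

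**2. Expected survivors at 18 months**

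From the three-year rates, S(18) = S(36)^0.5. From the medians, S(18) = 0.5^(18/median).

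| Source | Arm A | Arm B | Total alive |
|---|---|---|---|
| Three-year rates | 54.8% × 129 = 70.7 | 70.2% × 129 = 90.6 | 161.2 |
| Medians | 55.8% × 129 = 72.0 | 68.9% × 129 = 88.9 | 160.9 |
| Assumed in 8.6 | 89 | 89 | 178 |

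The two sets differ because the stated medians are not the direct conversion of the three-year rates, which would be 20.7 and 35.3 months. They match hazards diluted by 7.5% crossover in each direction. The two rows therefore cover survival with and without crossover.

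Completion needed to reach 89: Arm A, 89/70.7 = 126% or 89/72.0 = 124%; Arm B, 89/90.6 = 98% or 89/88.9 = 100%. Under exponential survival, the binomial chance of 89 or more alive in Arm A is 0.07% (rates) or 0.15% (medians).

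**3. Another reading of the 69%**

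If it applies only to the 85% who do not cross over, the count is 129 × 0.85 × 0.69 = 75.7 per arm, not 89.

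**4. Power with the attainable numbers (unadjusted t test)**

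All survivors complete, three-year rates: 4.5 / (14 × √(1/70.7 + 1/90.6)) = 4.5 / 2.222 = 2.025, and Φ(2.025 − 1.282) = 77.1%. The noncentral t gives 77.0% (77.1% from the medians).

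| Completion among survivors (assumed) | Power |
|---|---|
| 100% | 77% |
| 90% | 74% |
| 80% | 70% |
| 70% | 66% |

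The difference detectable with 79% power is 4.4 points at 89 per arm, 4.6 if all survivors complete and 5.2 at 80% completion.

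If local therapy does not prolong survival and both arms follow the control rate, 141–144 are alive in total and power is at most 73–74%.

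**5. Effect of adjusting for the randomization score**

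Adjusted SD = 14 × √(1 − ρ²).

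| Assumed ρ | All survivors complete | 80% complete |
|---|---|---|
| 0.4 | 82% | 76% |
| 0.5 | 85% | 79% |
| 0.6 | 89% | 84% |

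To regain 79%, completion among survivors must be about 90%, 80% and 69% at these three correlations, and about 97–98% at ρ = 0.3.

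**The case against.** The strongest objection is about weight. The documents alone support only a fall from 79% to about 77%, for a secondary endpoint tested at a two-sided level of 0.20. Every larger loss comes from completion rates the documents do not give. This stands, and the size of the point should be read accordingly. Some non-completion is foreseeable, though: 5.2 notes that the questionnaire exists only in English, and 5.2.1 allows patients to decline or to be too sick to answer.

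Second, the Arm A shortfall depends on constant hazard. Randomized patients are selected for no progression, so early mortality could be lower. With 30% alive at three years, a Weibull shape of about 1.7 would give 69% alive at 18 months. That is possible, but 8.4 states an exponential distribution, so the two sections still conflict. The 0.1% chance is conditional on that assumption and is not a forecast.

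Third, an unadjusted two-sample test is legitimate, 5.2 names no test, and the mixed model in 8.6 already includes the randomization scores. All true. The count error does not make the t test wrong. But the power statement is tied to that test, with Wilcoxon as the fallback, and neither uses the randomization score.

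Fourth, 8.6 provides for joint modelling when missingness is informative. That is an analysis method for data lost through death. It does not make 89 attainable in Arm A or correct the power.

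**Conclusion.** The point holds. The 89 per arm in 8.6 contradicts the survival assumptions in 8.4. About 161 patients are expected alive at 18 months against 178 assumed to have data, and the shortfall falls almost wholly on Arm A (71–72 against 89). The loss of power from deaths alone is small, to about 77%. It reaches 70% if one survivor in five does not return the form.

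The survivor counts rest on equal allocation, exponential survival from randomization and no loss to follow-up; any such loss would lower them further. Adjusting for the randomization score may recover the power, but this depends on a correlation the documents do not give and is not assured.

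**What to change.** 1. In 8.6, replace the single 89 with arm-specific numbers: 18-month survival from 8.4 (about 71–72 in Arm A and 89–91 in Arm B) multiplied by an explicit completion rate among survivors. Restate the power from those numbers. At 80% completion, for example, that is about 57 and 72 patients, with 70% power unadjusted.
2. Name the primary 18-month FACT-B TOI comparison as an analysis adjusted for the randomization score and the stratification factors in 4.2.5. Either an analysis of covariance or the 18-month contrast from the mixed model with time as categories would serve, in place of the unadjusted t test or Wilcoxon. State the correlation assumed in the power calculation, and say how this analysis relates to the joint model already provided for. Adjustment improves precision; it does not replace that provision for deaths.

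The first item is a wording correction, and the stated unadjusted power falls. The second is a small change to the analysis plan. Both use data already collected, and no visit or patient is added.
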